5.2.1.2.2 Trametinib Dose Modification

Please refer to Section 5.6.1.1.4.

5.2.1.2.3 Dabrafenib Dose Modification

Please refer to Section 5.6.1.1.4.

5.2.2 Timing of Dose Administration

A maximum of 28 days has been provided to screen subjects prior to first dose.

5.2.2.1 Pembrolizumab Dose Administration

Pembrolizumab should be administered every 21 days (for Q3W schedule) after all procedures and assessments have been completed except for the post-infusion PK sample time points listed in the Study Flow Chart. Pembrolizumab may be administered within 72 hours before or after the planned date of treatment for administrative reasons only (e.g., scheduling an infusion around a holiday).

The specific time of pembrolizumab administration (e.g., time of the week for first administration; time of the day for each administration) should take into consideration PK sampling time points and study visit procedures.

Pembrolizumab will be administered as a 30 minute IV infusion Q3W. Sites should make every effort to target infusion timing to be as close to 30 minutes as possible. However, given the variability of infusion pumps from site to site, a window of -5 minutes and +10 minutes is permitted (i.e., infusion time is 30 minutes: -5 min/+10 min). Subjects do not need to be observed for any specific period of time after the infusion, but should be provided instructions to notify study personnel if symptoms of infusion reaction occur after any pembrolizumab infusion.

The Procedures/Pharmacy Manuals contain specific instructions for pembrolizumab dose calculation, preparation of the infusion fluid, and administration.

5.2.2.2 Trametinib and Dabrafenib Dose Administration

Both trametinib and dabrafenib should be administered in the morning at approximately the same time every day. The second dose of dabrafenib should be administered approximately 12 hours after the morning dose. Study medication should be taken orally with approximately 200 mL of water under fasting conditions, either 1 hour before or 2 hours after a meal.

The specific time of trametinib and dabrafenib administration should take into consideration PK sampling time points and study visit procedures.

If a subject vomits after taking study medication, the subject should be instructed not to retake the dose and should take the next dose as originally scheduled.

If a subject misses a dose of dabrafenib, the subject may take the dose immediately if the next dose is scheduled for at least 6 hours later. If the next scheduled dose is due in less than 6 hours, the subject should skip the dose and resume dosing at the next scheduled dose.

If a subject misses a dose of trametinib, the subject may take the dose immediately if the next dose is scheduled for at least 12 hours later. If the next scheduled dose is due in less than 12 hours, the subject should skip the dose and resume dosing at the next scheduled dose.

Subjects should start treatment as soon as possible after randomization but no later than 72 hours post-randomization.

5.2.3 Trial Blinding/Masking

Parts 1, 2, 4, and 5 are open-label in the trial; therefore, the Sponsor, investigator and subject will know the treatment administered.

In Part 3, a double-blind/masking technique will be used. Pembrolizumab and placebo will be dispensed in a blinded fashion by an unblinded pharmacist or qualified trial site personnel.

The subject, the investigator and Sponsor personnel or delegate(s) who are involved in the treatment or clinical evaluation of the subjects are unaware of the group assignments.

5.2.4 Rules for Dose Escalation and Confirmation

5.2.4.1 Dose Escalation

5.2.4.1.1 Dose Escalation (Part 1)

Dose limiting toxicities (DLTs) observed in Cycle 1 (i.e., Cycle 1, initiated with the first pembrolizumab dose) will be used to determine escalation to the next dose level. The study is using a 3+3 design followed by dose confirmation based on the TPI method [92] and has 2 parts: a dose escalation part, and a dose confirmation part according to the TPI approach. The guidelines used for dose escalation and dose confirmation are shown in [Table 11](#).

The rules applied for the dose escalation part are as follows:

An initial cohort of 3 subjects is enrolled at Dose Level 1.

- If 0/3 subjects develops a DLT, then dose escalation will terminate with this finding, Dose Level 1 will be considered the preliminary MTD/MAD, and the study will proceed to the dose confirmation stage.
- If 1/3 subjects develops a DLT, another 3 subjects will be enrolled at this dose level.
 - If ≤ 1 of the 3 new subjects develops a DLT (for a total of $\leq 2/6$ subjects with a DLT at this dose level), then dose escalation will terminate with this finding, Dose Level 1 will be considered the preliminary MTD/MAD, and the study will proceed to the dose confirmation stage.
 - If > 1 of the 3 new subjects develop a DLT (for a total of $> 2/6$ subjects with a DLT at this dose level), 3 subjects will be enrolled at Dose Level -1.
 - If 0/3 subjects develops a DLT at Dose Level -1, then dose escalation will terminate with this finding, Dose Level -1 will be considered the preliminary MTD/MAD, and the study will proceed to the dose confirmation stage.
 - If 1/3 subjects develops a DLT at Dose Level -1, another 3 subjects will be enrolled at Dose Level -1. If $\leq 2/6$ subjects develop a DLT at Dose Level -1, then dose escalation will terminate with this finding, Dose Level -1 will be considered the preliminary MTD/MAD, and the study will proceed to the dose confirmation stage.
 - If $\geq 2/3$ subjects or $> 2/6$ subjects develop a DLT at Dose Level -1, the dose escalation part of the study will terminate and the combination will not be studied further.

- If $\geq 2/3$ subjects develop a DLT, 3 subjects will be enrolled in Dose Level -1.
 - If 0/3 subjects develops a DLT at Dose Level -1, then dose escalation will terminate with this finding, Dose Level -1 will be considered the preliminary MTD/MAD, and the study will proceed to the dose confirmation stage.
 - If 1/3 subjects develops a DLT at Dose Level -1, another 3 subjects will be enrolled at Dose Level -1. If $\leq 2/6$ subjects develop a DLT at Dose Level -1, then dose escalation will terminate with this finding, Dose Level -1 will be considered the preliminary MTD/MAD, and the study will proceed to the dose confirmation stage.
 - If $\geq 2/3$ subjects of $>2/6$ subjects develop a DLT at Dose Level -1, the dose escalation part will terminate and the combination will not be studied further.

[figure not shown]
It is conceptually acceptable to de-escalate to an intermediate, not pre-defined and not previously-studied dose, if evaluation of toxicity at such a dose is desired in lieu of proceeding directly to the dose confirmation stage of the study. If this approach is taken, 3 new subjects should be enrolled at the new intermediate dose, and the aforementioned rules should be used to determine further enrollment at this dose level.

There may be >3 or >6 subjects enrolled at any given dose cohort due to replacement of subjects who were not evaluable or further evaluation of safety or pharmacokinetics at a dose level.

5.2.4.1.2 Dose Escalation (Part 4)

Dose limiting toxicities (DLTs) observed in Cycle 1 (i.e., following the trametinib run-in period in Cycle 1, initiated with the first pembrolizumab dose) will be used to determine escalation to the next dose level. The study is using a 3+3 design followed by dose confirmation based on the modified Toxicity Probability Interval (mTPI) method [104] and has 2 parts: a dose escalation part, and a dose confirmation part according to the mTPI approach. The guidelines used for dose escalation ([Table 6](#) and [Table 7](#)) and dose confirmation ([Table 12](#) and [Table 13](#)) are provided. A flow diagram for the concurrent and intermittent regimens is included in [Figure 2](#).

Figure 2 Flow Diagram: Part 4 Concurrent (cDL) and Intermittent (iDL) Dose Levels

Each treatment regimen (concurrent and intermittent) will be tested simultaneously, and subjects will be assigned to these treatment arms using 1:1 randomization whenever both regimens are open for enrollment. For each regimen, an initial cohort of 3 subjects is enrolled at Dose Level 1. The dose levels for the concurrent and intermittent treatment arms are shown in Table 6 and Table 7, respectively. Of note, for the concurrent dosing regimen, Dose Levels 2a and 2b will be tested simultaneously, and to proceed to Dose Level 3, both Dose Level 2a and 2b must be found to be tolerable.

The rules applied for the dose escalation part are as follows:

- If 0/3 subjects develop a DLT, then dose escalation will advance to the next Dose Level(s).
- If 1/3 subjects develop a DLT, another 3 subjects will be enrolled at this dose level.
 - If ≤ 1 of the 3 new subjects develops a DLT (for a total of $\leq 2/6$ subjects with a DLT at this dose level), then dose escalation will advance to the next Dose Level(s). If this occurs at Dose Level 3 (concurrent regimen) or Dose Level 2 (intermittent regimen), then dose escalation will terminate with this finding,

the respective Dose Level will be considered the MTD/MAD, and the study will proceed to the dose confirmation stage.

- If >1 of the 3 new subjects develop a DLT at Dose Level 1 (for a total of >2/6 subjects with a DLT), 3 subjects will be enrolled at Dose Level -1a. If this occurs at any other dose level for either regimen, then dose escalation will terminate with this finding, the previous lower dose level will be considered the preliminary MTD, and the study will proceed to the dose confirmation stage.
 - If 0/3 subjects develop a DLT at Dose Level -1a, then dose escalation will advance to Dose Level -1b.
 - If 1/3 subjects develops a DLT at Dose Level -1a, another 3 subjects will be enrolled at Dose Level -1a. If $\leq 2/6$ subjects develop a DLT at Dose Level -1a, then dose escalation will advance to Dose Level -1b. Of note, if Dose Level -1b is subsequently found to be tolerable, the dose escalation will terminate with this finding, Dose Level -1b will be considered the preliminary MTD, and the study will proceed to the dose confirmation stage.
 - If $\geq 2/3$ subjects or >2/6 subjects develop a DLT at Dose Level -1a, the dose escalation part of the study will terminate and the dosing regimen will not be studied further.
- If $\geq 2/3$ subjects develop a DLT at Dose Level 1, 3 subjects will be enrolled in Dose Level -1a.
 - If 0/3 subjects develop a DLT at Dose Level -1a, then dose escalation will advance to Dose Level -1b. Of note, if Dose Level -1b is subsequently found to be tolerable, the dose escalation will terminate with this finding, Dose Level -1b will be considered the preliminary MTD, and the study will proceed to the dose confirmation stage.
 - If 1/3 subjects develop a DLT at Dose Level -1a, another 3 subjects will be enrolled at Dose Level -1a. If $\leq 2/6$ subjects develop a DLT at Dose Level -1a, then dose escalation will advance to Dose Level -1b. Of note, if Dose Level -1b is subsequently found to be tolerable, the dose escalation will terminate with this finding, Dose Level -1b will be considered the preliminary MTD, and the study will proceed to the dose confirmation stage.
 - If $\geq 2/3$ subjects or >2/6 subjects develop a DLT at Dose Level -1a, the dose escalation part will terminate and the combination will not be studied further.

It is conceptually acceptable to de-escalate to an intermediate, not pre-defined and not previously-studied dose, if evaluation of toxicity at such a dose is desired in lieu of proceeding directly to the dose confirmation stage of the study. If this approach is taken, 3

new subjects should be enrolled at the new intermediate dose, and the aforementioned rules should be used to determine further enrollment at this dose level.

There may be >3 or >6 subjects enrolled at any given dose cohort due to replacement of subjects who were not evaluable or further evaluation of safety or pharmacokinetics at a dose level.

Patients who experience a DLT will be allowed to remain on study if they meet the following criteria: (1) the investigator believes it is appropriate for patients to remain on study, and (2) the event has resolved and no longer meets the definition of DLT.

5.2.4.2 Dose Confirmation

5.2.4.2.1 Dose Confirmation (Part 2)

The objective of dose confirmation is to refine the estimate of the MTD. Dose confirmation involves the expansion of at least 1 dose combination studied in the dose escalation stage of the study.

Dose confirmation will begin with expansion of the preliminary MTD identified in the dose escalation stage described above. The dose confirmation part will continue based on the TPI method [92] until 14 subjects are studied at the selected dose (combined from dose escalation and dose confirmation) with ≤ 5 of 14 subjects experiencing a DLT. As subjects become evaluable for DLT assessment, the number of subjects who are evaluable for DLT versus the number of subjects who developed a DLT will be continuously assessed and de-escalation and re-escalation to eligible doses will occur as shown in [Table 11](#).

Table 11 Part 2 Dose Confirmation Rules

		Number of patients treated at current dose										
		4	5	6	7	8	9	10	11	12	13	14
Number of toxicities	0	E	E	E	E	E	E	E	E	E	E	E
	1	S	S	S	E	E	E	E	E	E	E	E
	2	D	S	S	S	S	S	S	E	E	E	E
	3	DU	DU	D	D	S	S	S	S	S	S	S
	4	DU	DU	DU	DU	DU	D	D	S	S	S	S
	5		DU	DU	DU	DU	DU	DU	D	D	D	S
	6			DU	DU	DU	DU	DU	DU	DU	DU	D
	7				DU	DU	DU	DU	DU	DU	DU	DU
	8					DU	DU	DU	DU	DU	DU	DU
	9						DU	DU	DU	DU	DU	DU
	10							DU	DU	DU	DU	DU
	11								DU	DU	DU	DU
	12									DU	DU	DU
	13										DU	DU
	14											DU

E = Escalate to the next higher dose
 S = Stay at the current dose
 D = De-escalate to the next lower dose
 DU = The current dose is unacceptably toxic

Target MTD = 25% a=1; b=1; k1=1.5; k2=0.5; pow=1.1 per [92]
--

If de-escalation to Dose Level -1 is required, but Dose Level -1 was not studied in the Part 1 of the study, 3+3 design rules described in Section 5.2.4.1 will be applied to Dose Level -1 before 0/3 or $\leq 2/6$ DLTs are observed at this dose and Dose Level -1 enters the dose confirmation stage with the rules shown in Table 11.

Subjects may be enrolled continuously (i.e., without waiting for Cycle 1 completion of subjects who have received the first dose) unless a DLT is observed at the particular dose. Once a DLT is observed, the number of subjects who are enrolled at that dose but are not yet fully evaluable for DLT assessment may not exceed the number of remaining subjects who are at risk of developing a DLT before the dose would be considered unacceptably toxic (denoted as DU in Table 11). For example, if 3/8 subjects have experienced a DLT at a given dose level, no more than an additional 2 subjects should be enrolled at this dose level until additional DLT data are available. This is because this dose level would be considered unacceptably toxic if all 2 additional subjects experience a DLT (i.e., 5/10 subjects with DLT in Table 11). To find out how many more subjects can be enrolled, one can count steps in diagonal direction (down and to the right) from the cell (8 subjects, 3 toxicities) to the first cell marked DU.

If enrollment expands to 14 subjects for a dose level, and ≤ 5 of the 14 subjects develop a DLT, then the dose confirmation will stop. If enrollment expands to 14 subjects for a dose level and $>5/14$ subjects develop a DLT, then the next lower dose may be expanded to further explore the dose-response relationship. Note that while 25% has been the target toxicity rate used to generate the guidelines in [Table 11](#), the observed rate of subjects with DLT at the MTD may be slightly above or below 25%.

5.2.4.2.2 Dose Confirmation (Part 5)

The objective of dose confirmation is to refine the estimate of the MTD. Dose confirmation involves the expansion of at least 1 dose combination studied in the dose escalation stage of the study.

Dose confirmation will begin with expansion of the preliminary MTD identified in the dose escalation stage described above. As in Part 4, each treatment arm (concurrent and intermittent) will be tested simultaneously, and subjects will be assigned to these treatment arms using 1:1 randomization whenever both regimens are open for enrollment. The dose confirmation part will continue based on the mTPI method [104] with a target DLT rate of 30% until 14 subjects are studied at the selected dose (combined from dose escalation and dose confirmation) with ≤ 6 of 14 subjects experiencing a DLT. As subjects become evaluable for DLT assessment, the number of subjects who are evaluable for DLT versus the number of subjects who developed a DLT will be continuously assessed and de-escalation and re-escalation to eligible doses will occur as shown in [Table 12](#). [Table 12](#) outlines the dose escalation and de-escalation sequences depending on the preliminary MTD defined in Part 4 for the concurrent and intermittent dosing regimens.

If, for example, de-escalation to Dose Level -1a is required, but Dose Level -1a was not studied in Part 4, the 3+3 design rules described in Section 5.2.4.1.2 will be applied to Dose Level -1a before (1) 0/3 or $\leq 2/6$ DLTs are observed at this dose, and, (2) Dose Level -1a enters the dose confirmation stage with the rules shown in [Table 13](#).

Table 12 mTPI Dosing Sequences

Concurrent Dosing Regimen		Intermittent Dosing Regimen	
Preliminary MTD from Part 4	Sequence	Preliminary MTD from Part 4	Sequence
cDL-1a	cDL-1a -> cDL-1b -> cDL1 -> cDL2a -> cDL3	iDL-1a	iDL-1a -> iDL-1b -> iDL1 -> iDL2
cDL-1b	cDL-1a <- cDL-1b -> cDL1 -> cDL2a -> cDL3	iDL-1b	iDL-1a <- iDL-1b -> iDL1 -> iDL2
cDL1	cDL-1a <- cDL1 -> cDL2a -> cDL3	iDL1	iDL-1a <- iDL1 -> iDL2
cDL2a	cDL-1a <- cDL1 <- cDL2a -> cDL3	iDL2	iDL-1a <- iDL1 <- iDL2
cDL2b	cDL-1a <- cDL1 <- cDL2b -> cDL3		
cDL3	cDL-1a <- cDL1 <- cDL2a <- cDL3		

Subjects may be enrolled continuously (i.e., without waiting for Cycle 1 completion of subjects who have received the first dose) unless a DLT is observed at the particular dose. Once a DLT is observed, the number of subjects who are enrolled at that dose but are not yet fully evaluable for DLT assessment may not exceed the number of remaining subjects who are at risk of developing a DLT before the dose would be considered unacceptably toxic (denoted as DU in Table 13). For example, if 3/8 subjects have experienced a DLT at a given dose level, no more than an additional 3 subjects should be enrolled at this dose level until additional DLT data are available. This is because this dose level would be considered unacceptably toxic if all 3 additional subjects experience a DLT (i.e., 6/11 subjects with DLT in Table 13). To find out how many more subjects can be enrolled, one can count steps in diagonal direction (down and to the right) from the cell (8 subjects, 3 toxicities) to the first cell marked DU.

If enrollment expands to 14 subjects for a dose level, and ≤ 6 of the 14 subjects develop a DLT, then the dose confirmation will stop. If enrollment expands to 14 subjects for a dose level and $>6/14$ subjects develop a DLT, then the next lower dose may be expanded to further explore the dose-response relationship. Note that while 30% has been the target toxicity rate used to generate the guidelines in Table 13, the observed rate of subjects with DLT at the MTD may be slightly above or below 30%.

Table 13 Part 5 Dose Confirmation Rules

Number of toxicities	Number of subjects treated at current dose											
	3	4	5	6	7	8	9	10	11	12	13	14
0	E	E	E	E	E	E	E	E	E	E	E	E
1	S	S	S	E	E	E	E	E	E	E	E	E
2	D	S	S	S	S	S	S	S	E	E	E	E
3	DU	DU	D	S	S	S	S	S	S	S	S	S
4		DU	DU	DU	D	D	S	S	S	S	S	S
5			DU	DU	DU	DU	DU	D	S	S	S	S
6				DU	DU	DU	DU	DU	DU	D	S	S
7					DU	DU	DU	DU	DU	DU	DU	D
8						DU	DU	DU	DU	DU	DU	DU
9							DU	DU	DU	DU	DU	DU
10								DU	DU	DU	DU	DU
11									DU	DU	DU	DU
12										DU	DU	DU
13											DU	DU
14												DU

E = Escalate to the next higher dose
S = Stay at the current dose
D = De-escalate to the next lower dose
DU = The current dose is unacceptably toxic
Target toxicity rate = 30%
Flat non-informative prior Beta (1,1) is used as a prior and $\epsilon_1=\epsilon_2=0.05$ [104].

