Upon identification of a preliminary maximum tolerated dose for both the concurrent and intermittent dosing regimens, each regimen will proceed to Part 5 for dose confirmation using a modified TPI (mTPI) design. In the event that tolerable concurrent and intermittent dosing regimens are identified, the Sponsor may choose to pursue one or both for dose confirmation in Part 5. For each regimen, a total of 14 subjects evaluable for DLT will be treated with the identified dose across Part 4 and 5 by the end of the dose confirmation. In the event that a tolerable dose for either dosing regimen of (MK+T) cannot be identified in Part 4, that particular dosing regimen will not be further explored in Part 5.

In Part 5, the expansion cohort(s) will be used to further evaluate safety and preliminary efficacy in the (MK+T) combination(s). Dose expansion requires only BRAF wild type [without V600E or K] melanoma to be enrolled. During the study it was found that the accrual of BRAF wild type melanoma subjects was limited, reflecting recent changes in the standard of care for these patients which include checkpoint inhibition in combination with

other drugs not compatible with this study design. The expansion cohort will not be pursued further following the completion of Part 5 dose confirmation.

Table 6 Parts 4 and 5: Concurrent (MK+T) Study Treatment Arm(s) and Escalation/De-Escalation Algorithm

Dose Level	Trametinib Monotherapy Run-In	Pembrolizumab	Trametinib	Dosing Regimen
cDL3	2 Weeks 2 mg QD	200 mg Q3W	2 mg QD	Concurrent dosing of pembrolizumab and trametinib starting at Week 3
cDL2b	4 Weeks 2 mg QD	200 mg Q3W	2 mg QD	Concurrent dosing of pembrolizumab and trametinib starting at Week 5
cDL2a	2 Weeks 1.5 mg QD	200 mg Q3W	1.5 mg QD	Concurrent dosing of pembrolizumab and trametinib starting at Week 3
cDL1	4 Weeks 1.5 mg QD	200 mg Q3W	1.5 mg QD	Concurrent dosing of pembrolizumab and trametinib starting at Week 5
cDL-1b	4 Weeks 2 mg QD	200 mg Q3W	2 mg QD	pembrolizumab dosing starting at Week 5 with intermittent 2 weeks OFF trametinib/2 weeks ON trametinib
cDL-1a	4 Weeks 1.5 mg QD	200 mg Q3W	1.5 mg QD	pembrolizumab dosing starting at Week 5 with intermittent 2 weeks OFF trametinib/2 weeks ON trametinib

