
Start at cDL1. If cDL1 is tolerated, test cDL2a and cDL2b concurrently. If cDL2a and cDL2b both tolerated, test cDL3. If cDL3 is tolerated, preliminary MTD is cDL3. If cDL3 is not tolerated, preliminary MTD is cDL2a. If cDL2a is tolerated and cDL2b is not tolerated, preliminary MTD is cDL2a. If cDL2b is tolerated and cDL2a is not tolerated, preliminary MTD is cDL2b. If cDL2a and cDL2b both not tolerated, preliminary MTD is cDL1. If cDL1 is not tolerated, test cDL-1a. If cDL-1a is tolerated, test cDL-1b. If cDL-1b is tolerated, preliminary MTD is cDL-1b. If cDL-1b is not tolerated, preliminary MTD is cDL-1a. If cDL-1a is not tolerated, no tolerable dose for the regimen is identified.
				

Table 7 Parts 4 and 5: Intermittent (MK+T) Study Treatment Arm(s) and Escalation/De-Escalation Algorithm

Dose Level	Trametinib Monotherapy Run-In	Pembrolizumab	Trametinib	Dosing Regimen
iDL2	2 Weeks 2 mg QD	200 mg Q3W	2 mg QD	pembrolizumab dosing starting at Week 3 with intermittent 1 week OFF trametinib/2 weeks ON trametinib
iDL1	2 Weeks 1.5 mg QD	200 mg Q3W	1.5 mg QD	pembrolizumab dosing starting at Week 3 with intermittent 1 week OFF trametinib/2 weeks ON trametinib
iDL-1b	2 Weeks 2 mg QD	200 mg Q3W	2 mg QD	pembrolizumab dosing starting at Week 3 with intermittent 2 weeks OFF trametinib/2 weeks ON trametinib
iDL-1a	2 Weeks 1.5 mg QD	200 mg Q3W	1.5 mg QD	pembrolizumab dosing starting at Week 3 with intermittent 2 weeks OFF trametinib/2 weeks ON trametinib

Start at iDL1. If iDL1 is tolerated, test iDL2. If iDL2 is tolerated, preliminary MTD is iDL2. If iDL2 is not tolerated, preliminary MTD is iDL1. If iDL1 is not tolerated, test iDL-1a. If iDL-1a is tolerated, test iDL-1b. If iDL-1b is tolerated, preliminary MTD is iDL-1b. If iDL-1b is not tolerated, preliminary MTD is iDL-1a. If iDL-1a is not tolerated, no tolerable dose for the regimen is identified.
				

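### Table 12 steps from cDL2b up to cDL3 in Part 5, although cDL2b is the preliminary MTD only when cDL2a has failed; the row should end at cDL2b

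*Combined protocol and SAP*

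**What the plan says.** **Part 4 (escalation).** Section 5.2.4.1.2 says that "to proceed to Dose Level 3, both Dose Level 2a and 2b must be found to be tolerable". The algorithm under Table 6 in Section 2.1 has the same rule: "If cDL2a and cDL2b both tolerated, test cDL3". Its other branches fix the preliminary MTD: "If cDL2b is tolerated and cDL2a is not tolerated, preliminary MTD is cDL2b", and "If cDL2a is tolerated and cDL2b is not tolerated, preliminary MTD is cDL2a". If both are tolerated and cDL3 then fails, the preliminary MTD is cDL2a. Table 6 is titled "Parts 4 and 5: Concurrent (MK+T) Study Treatment Arm(s) and Escalation/De-Escalation Algorithm".

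**The levels (Table 6).** All use pembrolizumab 200 mg Q3W.
- cDL2a: 2-week run-in, trametinib 1.5 mg.
- cDL2b: 4-week run-in, trametinib 2 mg.
- cDL3: 2-week run-in, trametinib 2 mg.

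**Part 5 (confirmation).** Section 5.2.4.2.2 says that "de-escalation and re-escalation to eligible doses will occur as shown in" Table 12. For a preliminary MTD of cDL2b that table gives "cDL-1a <- cDL1 <- cDL2b -> cDL3". Table 13 supplies the signal: E (escalate), S (stay), D (de-escalate) or DU (unacceptably toxic). The section does not define which doses are eligible.

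**The concern.** Table 12 is keyed to the Part 4 result. A subject reaches the cDL2b row only because cDL2a was rejected, and the row does not include cDL2a. On an E signal the next subjects go to cDL3, which has not been studied at that point. It shares the rejected level's run-in length and has a higher trametinib dose. More data at cDL2b, with its longer run-in, do not show that the 2-week run-in is tolerable.

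This differs from mTPI returning to a level that failed in Part 4. In that case the failed level itself receives new data. Here it is bypassed. The Part 4 rules would have kept cDL3 closed on the same results, and the reader is not told why Part 5 should open it.

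**Working it through.** **1. When does the cDL2b row apply?** All outcomes under the Table 6 algorithm, given cDL1 tolerated:

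| cDL2a | cDL2b | cDL3 | Preliminary MTD | Part 4 condition for cDL3 |
|---|---|---|---|---|
| tolerated | tolerated | tolerated | cDL3 | met |
| tolerated | tolerated | not tolerated | cDL2a | met |
| tolerated | not tolerated | not tested | cDL2a | not met |
| not tolerated | tolerated | not tested | **cDL2b** | **not met** |
| not tolerated | not tolerated | not tested | cDL1 | not met |

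Only one outcome leads to cDL2b. In it the condition fails and cDL3 is untested.

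**2. Does Table 13 reproduce?** Yes. mTPI with target 0.30, both epsilons 0.05 and a Beta(1,1) prior gives all 114 filled cells. The DU cut-off, P(rate > 0.30) > 0.95, is my assumption, because the protocol does not state it. A level passes Part 4 with 0/3, 1/6 or 2/6 DLTs, which Table 13 reads as E, E and S.

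**3. How often does the row open cDL3?** The documents give no DLT rates, so the rates are assumed and the levels taken as independent. Let p be the true rate and q = 1 − p.

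Probability of being tolerated under 3+3:

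T(p) = q³ + 3pq²(q³ + 3pq²), where the parts are 0/3 (q³), 1/6 (3pq² × q³) and 2/6 (3pq² × 3pq²).

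For p = 0.2: 0.512 + 0.384 × 0.896 = 0.856.

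Probability of an E at cDL2b, from Table 13 as printed. At least one further subject (or three) is added first, and a path ends at D, DU or n = 14. With three DLTs Table 13 never reads E, and with two it first reads E at n = 11.

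| Start | Read after each subject | Read in threes (n = 6, 9, 12) |
|---|---|---|
| 0/3 | q + p(q² + 2pq⁶) | q³ + 3pq² + 3p²q × q⁶ |
| 1/6 | q + pq⁴ | q³ + 3pq² × q³ |
| 2/6 | q⁵ | q⁶ |

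For p = 0.2, read singly: 0.949, 0.882 and 0.328. Weighting by 0.512, 0.197 and 0.147 and dividing by 0.856 gives P(E) = 0.827.

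The row opens cDL3 with probability (1 − T at cDL2a) × (T at cDL2b) × P(E at cDL2b). With equal rates:

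| p | T | T(1 − T) | P(E) singly | Row, singly | P(E) threes | Row, threes |
|---|---|---|---|---|---|---|
| 0.2 | 0.856 | 0.123 | 0.827 | 0.102 | 0.759 | 0.093 |
| 0.3 | 0.689 | 0.214 | 0.649 | 0.139 | 0.543 | 0.116 |
| 0.4 | 0.496 | 0.250 | 0.482 | 0.121 | 0.364 | 0.091 |

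With unequal rates:
- cDL2a 40%, cDL2b 20%: 0.504 × 0.856 = 0.432; times 0.827 or 0.759 gives 0.357 or 0.327.
- cDL2a 20%, cDL2b 40%: 0.144 × 0.496 = 0.071; times 0.482 or 0.364 gives 0.034 or 0.026.

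Subjects still under observation when a signal is read are ignored.

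**The case against.** **The condition belongs to Part 4.** Section 5.2.4.1.2 assigns Tables 6 and 7 to escalation and Tables 12 and 13 to confirmation, and the sentence requiring both levels sits in the Part 4 section. The Parts 4 and 5 title of Table 6 fits its role as the list of levels for both parts. This stands. A reader might infer that the protocol formally forbids cDL3 in Part 5 and that Table 12 breaks a binding rule; the documents do not go that far. What remains is that this row reverses the Part 4 logic without a stated reason.

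**mTPI is meant to revisit 3+3 rejections.** It is, and other rows do so, for example iDL1 to iDL2. A level rejected at 3/6 reads S in Table 13, and at the equal rates above 3/6 makes up about a quarter of Part 4 failures (0.256, 0.268, 0.247). But this row does not revisit cDL2a. A rejection at 2/3, 3/3 or 4/6 reads D or DU.

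**Safeguards exist.** The passage beginning "If, for example, de-escalation to Dose Level -1a is required, but Dose Level -1a was not studied in Part 4" could be extended so that cDL3 starts under 3+3, and Table 13 de-escalates at 2/3 and stops at 3/3. These rules govern how cDL3 is tested once open. They do not say whether it should be opened after cDL2a failed. The undefined term for eligible doses could exclude cDL3, but the arrow would then be wrong.

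**The cDL2a row.** A reader might extend the point to cDL2a → cDL3 when cDL2b failed. The documents do not support that. The cDL2a row also applies when both levels passed, and the rows from cDL-1a, cDL-1b and cDL1 all reach cDL3 through cDL2a without visiting cDL2b. Barring the step from cDL2a would make the ceiling tighter when only cDL2b failed than when both failed.

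**Conclusion.** The cDL2b row is wrong as written. Whenever it applies, cDL2a has failed, cDL2a is not re-tested, and the next level up is untested with the same run-in and more trametinib. Every other row that reaches cDL3 from below starts at cDL2a or passes through it. Severity is minor to should-fix. Confidence is moderate, because the entry condition is written for Part 4.

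Under the assumed rates the row opens cDL3 in about 9% to 14% of cases when the rates are equal. That becomes 36% (singly) or 33% (in threes) when cDL2a is at 40% and cDL2b at 20%, and about 3% with those two rates reversed. All figures are conditional on cDL1 being tolerated.

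A reader might take these as the chance of exposing subjects to an over-toxic dose. They are not: they count how often the path opens. At 20% or 30% the rejected cDL2a is in truth at or below the 30% target, so its rejection was chance. The documents give no data on run-in length and toxicity, and nothing in them shows that cDL2b became the preliminary MTD.

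**What to change.** In Table 12, end the row for preliminary MTD = cDL2b at that level (cDL-1a <- cDL1 <- cDL2b), and note that an E signal at cDL2b means stay. Leave the cDL2a row and the rows starting at cDL1 or below unchanged.

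This removes one arrow and adds one note, with no extra subjects or procedures. The probability of reaching cDL3 through this row falls to zero. The cost is that cDL3 cannot be reached in Part 5 from cDL2b. If the sponsor wants to keep that route, Section 5.2.4.2.2 should say so and give the reason for passing over a failed cDL2a.
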